**Table 11: Probability of stopping**

Operating characteristics of Stopping Rule			
Probability of DLT	Probability of Crossing Boundary	Probability of Stopping Before the Last Patient	Expected Sample Size
0.15	0.098	0.098	43.3
0.20	0.304	0.304	38.3
0.25	0.586	0.586	31.1
0.30	0.818	0.818	23.6
0.35	0.942	0.942	17.7
0.40	0.987	0.987	13.7

## 12 STATISTICAL CONSIDERATIONS

### 12.1 Sample Size Determination

#### Part 1

Part 1 has a maximum of 18 patients. Part 1 has a 3+3 dose de-escalation design with 3 doses and a maximum of 6 patients per dose.

#### Part 2

The sample size for Part 2 is 16-46 patients with 6 patients carried over from Part 1 at the RP2D. Simon’s optimal two-stage design will be used in Part 2. The primary outcome is the overall response rate (CR + PR) at 24 weeks. Withdrawal or progression prior to 24 weeks or missing 24-week assessment will be considered non-response. After the first 16 patients treated at the RP2D complete 24 weeks of therapy or meet treatment discontinuation criteria, enrollment will be put on hold and an interim analysis will be conducted. This study treatment will be considered promising if the overall response rate at 24 weeks is  $\geq 60\%$  and unacceptable if the overall response rate at 24 weeks is  $\leq 40\%$ . 50% is the reported best overall response rate of current first-line therapy with high-dose steroids. The null hypothesis that the true response rate is  $\leq 40\%$  will be tested against a one-sided alternative.

In the first stage of the dose-expansion study, 16 patients will be accrued and followed through the first 24 weeks of treatment. Of those 16 patients, 6 patients will be carried over from Part 1 at the RP2D. In recognition of a potential accrual pause of at least 24 weeks if all 16 patients are required to complete six months of combination therapy, we will permit enrollment of an additional 3 patients (20%) after the first 10 eligible patients in the first stage of the dose-expansion study are enrolled if no more than 5 of 16 patients have experienced treatment failure (i.e. addition of secondary systemic therapy or disease relapse or death) by the end of week 12 of treatment. If there are 7 or fewer responses in the first 16 patients enrolled, the study will be stopped. Otherwise, 30 additional patients

will be accrued for a total of 46. The null hypothesis will be rejected if 24 or more responses are observed in 46 patients. This design yields a type I error rate of 0.0486 and a power of 80% when the true response rate is  $\geq 60\%$ .

## **12.2 Population for analyses**

### **12.2.1 Part 1 DLT Evaluation**

Subjects must have received  $\geq 60\%$  of planned itacitinib doses (21 doses) and ECP treatments (4 treatments) during the DLT evaluation period or have had a DLT to be evaluable for dose tolerability.

### **12.2.2 Evaluable for toxicity**

All patients who have received at least one dose of itacitinib will be evaluable for toxicity assessment.

### **12.2.3 Evaluable for response**

Patients who have received at least two weeks of combined ECP and itacitinib administration will be evaluable for efficacy endpoints.

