### **Part 2**

Participants will not be replaced unless they fail to begin study treatment.

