## **12.4 Statistical Analysis**

### **12.4.1 Primary Endpoint Analysis**

#### **Part 1**

The primary objective is to assess the safety and tolerability of itacitinib and ECP in subjects with chronic GVHD and to determine the RP2D. Adverse events (AEs), serious adverse events (SAEs), and dose-limiting toxicities (DLTs) are primary endpoints.

All subjects who receive any study treatment will be included in the final summaries and listings of safety data. Detailed information collected for each AE will include a description of the event, duration, severity, relatedness to study drugs, action taken, and clinical outcome. The severity of the AEs will be graded according to the CTCAE v5.0. The statistical analysis of the safety data will be descriptive and tabular in nature.

## Part 2

Simon's optimal two-stage design will be used in Part 2. The primary outcome is the overall response rate (CR + PR) at 24 weeks. Withdrawal or progression prior to 24 weeks or missing 24-week assessment will be considered non-response. After the first 16 patients treated at the RP2D complete 24 weeks of therapy or meet treatment discontinuation criteria, enrollment will be put on hold and an interim analysis will be conducted. This study treatment will be considered promising if the overall response rate at 24 weeks is  $\geq 60\%$  and unacceptable if the overall response rate at 24 weeks is  $\leq 40\%$ . 50% is the reported best overall response rate of current first-line therapy with high-dose steroids. The null hypothesis that the true response rate is  $\leq 40\%$  will be tested against a one-sided alternative.

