In the first stage of the dose-expansion study, 16 patients will be accrued and followed through the first 24 weeks of treatment. Of those 16 patients, 6 patients will be carried over from Part 1 at the RP2D. In recognition of a potential accrual pause of at least 24 weeks if all 16 patients are required to complete six months of combination therapy, we will permit enrollment of an additional 3 patients (20%) after the first 10 eligible patients in the first stage of the dose-expansion study are enrolled if no more than 5 of 16 patients have experienced treatment failure (i.e. addition of secondary systemic therapy or disease relapse or death) by the end of week 12 of treatment. If there are 7 or fewer responses in the first 16 patients enrolled, the study will be stopped. Otherwise, 30 additional patients will be accrued for a total of 46. The null hypothesis will be rejected if 24 or more responses are observed in 46 patients. This design yields a type I error rate of 0.0486 and a power of 80% when the true response rate is  $\geq 60\%$ .

Exact binomial confidence intervals for response will be reported at the end of the trial.

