## Efficacy

- Overall response rate at 1-year as determined by the NIH Consensus Development Project Criteria, without secondary systemic immunosuppression and no recurrent malignancy or death
- Failure Free Survival (FFS) at 24 weeks and 1-year as defined as the time from the initiation of study therapy until treatment failure defined as the initiation of secondary therapy for chronic GVHD, malignancy relapse, or death from any cause.
- The proportion of patients who have withdrawn all immunosuppressants at 1-year.
- Overall response rate at 24 weeks, as determined by the NIH Consensus Development Project Criteria, stratified by concurrent prednisone (or equivalence) use: 0 mg/kg/d,  $\leq 0.25$ mg/kg/d, and  $> 0.25$ mg/kg/d.
- The mean cumulative prednisone dose used at 24 weeks.
- Organ-specific response rates at 24 weeks and 1-year as determined by the NIH Consensus Development Project Criteria.
- Change in NIH global score of chronic GVHD from baseline to 24 weeks and 1-year after the initiation of the protocol therapy. The NIH global score will be defined by using the NIH consensus criteria for the assessment of chronic GVHD severity.
- Duration of response (DOR), defined as the interval between the date of initial documentation of a response (PR or better), and the time of progression from the best response, the start of a new therapy for cGVHD (including corticosteroids), or death from any cause.
- Provider-reported chronic GVHD severity at baseline, 24 weeks, and 1-year.
- Patient-reported chronic GVHD severity at baseline, 24 weeks, and 1-year.
- 24 week and 1-year non-relapse mortality (NRM) defined as the proportion of participants who died due to causes other than a relapse of their primary hematologic disease.
- Relapse rate (RR) of malignant and non-malignant hematologic diseases, defined as the proportion of participants whose underlying disease relapses at 24 weeks and 1-year.
- Overall survival (OS) as defined as the time from the initiation of study therapy until death from any cause at 24 weeks and 1 year.

Observed proportions and exact binomial confidence intervals will be reported for binary endpoints with no censored events. These may include withdrawal from immunosuppressants at 1-year, the overall response at 24 weeks stratified by current prednisone use (0 mg/kg/d,  $\leq 0.25$ mg/kg/d, and  $> 0.25$ mg/kg/d.), the overall response at 1 year, organ-specific response at 24 weeks and 1 year, no recurrent malignancy, no

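### Section 12.2.3 limits efficacy endpoints to patients with two weeks of combined therapy, against the primary-endpoint non-response rule; applied to the reported ORR and its exact CI, it would drop plan-defined non-responders and bias both upward

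*Combined protocol and SAP*

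**What the plan says.** Section 12.2.3 (Evaluable for response) defines the efficacy set by exposure: "Patients who have received at least two weeks of combined ECP and itacitinib administration will be evaluable for efficacy endpoints". It makes no exception for the primary endpoint.

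The primary-endpoint text, given in the Study Summary, 12.1 and 12.4.1, handles early loss differently: "Withdrawal or progression prior to 24 weeks or missing 24-week assessment will be considered non-response". No minimum exposure is attached.

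The decision rules in 12.1 and 12.4.1 are stated as counts. For stage 1: "If there are 7 or fewer responses in the first 16 patients enrolled, the study will be stopped". For the final analysis: "The null hypothesis will be rejected if 24 or more responses are observed in 46 patients".

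Two further statements concern conduct rather than the analysis set. The interim is timed as follows: "After the first 16 patients treated at the RP2D complete 24 weeks of therapy or meet treatment discontinuation criteria". On replacement in Part 2, 12.3 says: "Participants will not be replaced unless they fail to begin study treatment".

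For estimation, 12.4.1 says only: "Exact binomial confidence intervals for response will be reported at the end of the trial". It names neither the denominator nor the confidence level.

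**The concern.** The two rules classify the same patient differently. Someone who withdraws or dies after one week of combined therapy is a non-responder under 12.4.1 and not evaluable under 12.2.3. Two analysts could each follow the plan and report different response rates.

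The exclusion window is longer than two weeks from first dose. The itacitinib lead-in of 5 to 10 days (Table 7, footnotes 2 and 26) does not count as combined therapy.

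What is at stake is the reported estimate. This is a single-arm trial whose Study Summary sets the result against historical response rates to high-dose steroids, so the ORR and its interval carry the comparison. Leaving the denominator open allows it to be chosen after the data are seen, and for early withdrawals the two-week set gives the more favourable figure.

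**Working it through.** **Inputs.** From 12.1 and 12.4.1: stop if 7 or fewer of 16 respond; reject if 24 or more of 46 respond; null rate 40%, alternative 60%; stated type I error 0.0486 and power 80%. From Table 7: a lead-in of 5 to 10 days. Not in the documents and therefore assumed: the number k of patients who leave before two weeks of combined therapy, taken as 0 to 4 of 46 (0 to 8.7%), and the confidence level, taken as two-sided 95% with 90% as an alternative.

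**Step 1. Reproduce the design.** The probability of rejection at true rate p is the sum over x = 8 to 16 of P(X₁ = x; 16, p) × P(X₂ ≥ 24 − x; 30, p).

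- p = 0.40: 0.0486, as stated.
- p = 0.60: 0.8006, as stated (80%).

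The cut-offs are responder counts. Removing non-responders from a denominator leaves those counts, and so the decision, unchanged.

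**Step 2. Exclusion window.** Lead-in plus 14 days of combined therapy: 5 + 14 = 19 days to 10 + 14 = 24 days after the first itacitinib dose.

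**Step 3. Effect on the reported ORR.** Take 24 responders, the rejection cut-off, and remove k early stoppers who are non-responders by the plan's rule. The estimate becomes 24/(46 − k), with Clopper-Pearson limits.

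| k removed | n | ORR | 95% CI | 90% CI |
|---|---|---|---|---|
| 0 | 46 | 52.2% | 36.9–67.1% | 39.2–65.0% |
| 1 | 45 | 53.3% | 37.9–68.3% | 40.1–66.2% |
| 2 | 44 | 54.5% | 38.8–69.6% | 41.1–67.5% |
| 3 | 43 | 55.8% | 39.9–70.9% | 42.2–68.8% |
| 4 | 42 | 57.1% | 41.0–72.3% | 43.3–70.2% |

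The estimate and both limits rise with each removal. The largest shift in this range is 57.1 − 52.2 = 4.9 points. The lower limit passes the 40% null rate at k = 4 with a 95% interval and at k = 1 with a 90% interval. For scale, the 95% half-width at n = 46 is (67.1 − 36.9)/2 = 15.1 points.

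**Step 4. When the direction does not hold.** Section 12.2.3 excludes on combined exposure, not on withdrawal. If one excluded patient is a responder, 24/46 (52.2%) becomes 23/45 (51.1%), and a count taken in the two-week set is 23, one short of the cut-off.

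**The case against.** The best defence is that the primary endpoint already has its own rule, stated three times, and that a specific rule normally governs over a general evaluability sentence. On that view the plan needs reconciling and no bias has been shown. Much of this stands. The enrolled counts, the interim timing (patients who meet discontinuation criteria remain among the 16) and the bar on replacement all support an all-treated denominator. But the section that defines the populations says otherwise, and nothing states which text prevails or which denominator the interval uses. The non-response rule could also be read as applying only within the evaluable set, though that sits badly with counting patients as enrolled.

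The size is hypothetical, and this objection also stands. Exclusion requires loss within about three and a half weeks of first dose, in patients whose life expectancy must exceed 24 weeks. One loss moves the ORR by 1.1 points.

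Four stronger readings are tempting, but the documents do not support them:

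- *Exclusion can only raise the ORR.* A patient who stops ECP in the first week but stays on itacitinib lacks two weeks of combined therapy. Section 6.7.1 does not expressly list stopping ECP alone as a reason to come off treatment; its noncompliance item is left to the investigator's opinion. Such a patient could still respond at week 24, and would then be removed as a responder.
- *The Simon type I error is inflated.* That would need the 16 and 46 to be filled with two-week-evaluable patients. Early exit of 2%, 5%, 10% or 15% would then give type I error of 0.061, 0.084, 0.143 or 0.233, taking a true 40% rate among all treated. The counts as written, and the bar on replacement once treatment has begun, do not allow this.
- *Early deaths and failures drop out of overall survival (OS), failure-free survival (FFS) and non-relapse mortality (NRM).* Section 12.4.2 lists these under Efficacy, so the literal wording reaches them. However, 12.2.3 is headed as evaluability for response, and OS and FFS run from the start of study therapy; OS, for example, is "the time from the initiation of study therapy until death from any cause at 24 weeks and 1 year".
- *The interim timing and replacement rules also contradict 12.2.3.* They govern conduct and support the all-treated reading, but they do not set the denominator of the ORR.

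**Conclusion.** The conflict is real and should be fixed. It lies between 12.2.3 on one side and the non-response rule and the enrolled counts on the other. If 12.2.3 is applied to the ORR and its exact interval, early stoppers who are non-responders under the plan leave the denominator, and the estimate and both limits are biased upward. The bias is between 0 and 4.9 points at 24 responders, for an assumed 0 to 4 early stoppers of 46, and is nil if nobody stops early.

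The conclusion is conditional in two ways. The upward direction holds for excluded patients who are non-responders, not for every patient whom 12.2.3 could exclude. The Simon decision keeps its type I error of 0.0486 and power of 0.80 provided responders are counted out of the 16 and 46 as written and no responder is excluded for short combined exposure. For OS, FFS and NRM the point is one of consistent wording; an established bias cannot be claimed.

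**What to change.** State in 12.2.3 and 12.4.1 that the Simon decisions, the ORR and its exact interval use all 16 and 46 counted patients who began study treatment at the RP2D, and that anyone without a qualifying 24-week response is scored as a non-responder. Keep the two-week combined-exposure set only as a labelled supportive analysis. For consistency, add that OS, FFS and NRM use all patients who began study treatment.

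This costs a few sentences. Sample size, enrolment counts, decision rules and patient management stay as they are. The downside is a slightly lower reported ORR than the two-week set would give when early stoppers are non-responders.

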## **12.3 Replacement of Participants**

### **Part 1**

Any participant who withdraws from the treatment before the completion of the DLT evaluation observation period for any reason other than a DLT may be replaced to ensure a minimum number of evaluable participants. Participants who do not maintain  $\geq 60\%$  study therapy compliance during the DLT evaluation period and participants who have a dose reduction due to concomitant medication use will be replaced.

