**Table 2: 3+3 Dose de-escalation design**

Number of patients with DLT at a given dose level	De-escalation Rules
0 out of 3	Enroll 3 patients at the same dose level
1 out of 3	Enter 3 more patients at the same dose level 
 
If 1 out of 6 patients experiences a DLT, identify the dose level as the RP2D.
 

	
 
If <math>\geq 2</math> out of 6 patients experience a DLT, this dose level exceeds the MTD. Enroll 3 patients at the next lower dose level (if available).
 

$\geq 2$ of 3	This dose level exceeds the MTD. Enroll 3 patients at the next lower dose level (if available).
In order for a dose level to be declared the RP2D, 6 patients must be treated at that dose level with $\leq 1$ DLT observed.	

Treatment will initiate at an itacitinib oral dose of 200 mg daily (Cohort 1). If zero or one out of three patients have a dose-limiting toxicity (DLT), three additional patients will be accrued to Cohort 1. If a DLT occurs in one-third or more of the total cohort, cohort de-escalation will be required and three patients will be accrued to Cohort -1. If  $\geq$  two DLTs occur in the first three subjects in Cohort -1, three patients will be accrued at the Cohort -2 dose level with the same safety parameters. If six patients are ultimately treated at dose Cohort -2 and  $\geq$  two DLTs occur, the trial will be stopped and the combination will be deemed unsafe. The dose level in which  $\leq$  one patient out of six experiences a DLT (as defined in Section 4.3), in accordance to the 3+3 de-escalation rules (as described in Table 2), will be declared the RP2D.

Subjects must have received  $\geq 60\%$  of planned INCB039110 (21 doses) and ECP treatments (4 treatments) during the DLT observation period to be evaluable for dose tolerability. Patients who miss  $> 40\%$  of planned itacitinib doses or ECP treatments within the DLT evaluation period for any reason other than for the management of treatment-related toxicities, will not be evaluable and will be replaced.

If a subject experiences a DLT, the toxicity should be managed per Section 7. The subject may remain on study therapy if deriving clinical benefit as assessed by the treating investigator.

**Review and approval from the primary medical monitor and DSMC are required prior to all cohort expansions and dose escalations.**

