### **6.2.3 Accountability and Compliance**

A patient dosing diary will be provided to the patients to aid in patient compliance with the dosing instructions. The diary will be maintained by the patient to include missed or changed itacitinib doses. The time of each dose administration and the number of tablets taken each day will be recorded in the dosing diary. Patients will be required to return the completed patient dosing diary on Day 1 of every cycle for timely review by site personnel and discussion of missed doses and/or compliance issues.

Patients will also be required to return all unused itacitinib tablets at the end of every cycle. The number of tablets returned by the patient will be counted, documented, and recorded by site personnel and reconciled with the patient's dosing diary to support the itacitinib accountability process. Excess or unused study drug returned to the investigative site will be destroyed in accordance with GCP after drug accountability has been performed.

Treatment compliance (reported as a percent) will be defined as the number of tablets or capsules taken during the study divided by the expected number of tablets or capsules, multiplied by 100%.

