### **7.1 Dose Modifications during the DLT period**

Dose reductions of itacitinib are not allowed during the DLT period unless a DLT has been confirmed for a specific patient. Dose reduction due to a drug-drug interaction (i.e. potent CYP3A4 inhibitors) will not be considered a DL, but these subjects will not be considered evaluable for DLT and will be replaced. If a subject experiences toxicity that meets DLT criteria during the DLT observation window, the patient should be taken off treatment. If the treating investigator feels that the patient is deriving clinical benefit, the patient may remain on study therapy only after discussion with and approval from the Principal Investigator.

After completion of the DLT observation period, dose modifications are allowed for patients who do not tolerate the protocol-specified itacitinib dosing to allow the patient to continue the study treatment. Dose modification guidelines are described below.

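### Part 1's evaluability and replacement rules contradict each other for patients with a DLT, and replacing one such patient can change the RP2D

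*Combined protocol and SAP*

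**What the plan says.** Five places bear on who counts in the 3+3.

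- **12.2.1** gives two routes to evaluability: reaching the 60% treatment threshold, "or have had a DLT to be evaluable for dose tolerability". The second route has no dose requirement.
- **12.3, Part 1, first sentence** covers withdrawal before the evaluation period ends. A participant who withdraws "for any reason other than a DLT may be replaced to ensure a minimum number of evaluable participants". This is permissive, and a DLT withdrawal is outside it.
- **12.3, Part 1, second sentence** covers participants short of 60%, and a second group: "study therapy compliance during the DLT evaluation period and participants who have a dose reduction due to concomitant medication use will be replaced". This is mandatory and mentions neither a DLT nor toxicity.
- **7.1** says that a reduction for a drug interaction is not a DLT, but that "these subjects will not be considered evaluable for DLT and will be replaced". It also sets the default after a DLT: "If a subject experiences toxicity that meets DLT criteria during the DLT observation window, the patient should be taken off treatment". A patient judged to be benefiting may stay on with the Principal Investigator's approval.
- **4.2** first requires 60% of planned treatment with no exception. It then says that patients missing more than 40% "for any reason other than for the management of treatment-related toxicities, will not be evaluable and will be replaced".

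Section 6.2.3 defines compliance as the "number of tablets or capsules taken during the study divided by the expected number of tablets or capsules", as a percentage. The reason for a missed dose plays no part. Table 2 requires six patients at a level with at most one DLT before that level can be the RP2D.

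**The concern.** The rules disagree for the patients the 3+3 most needs to count. Three situations arise.

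1. **A DLT patient stays on therapy with doses held and ends below 60%.** This patient has not withdrawn, so the first sentence of 12.3 gives no protection. The second sentence requires replacement, while 12.2.1 counts the patient.
2. **A DLT patient also has an interaction-driven reduction in the window.** For example, a related Grade 3 infection lasting more than 7 days is a DLT under Table 3. If a potent CYP3A4 inhibitor is then required, 6.6.3 recommends a lower itacitinib dose. Sections 7.1 and 12.3 replace the patient, while 12.2.1 counts the DLT.
3. **A patient is stopped by an early DLT.** The first sentence of 12.3 keeps this patient. The second, if compliance is measured against all planned doses, replaces the same patient.

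The DLT rate is the primary endpoint of Part 1. The selected dose goes to 40 further patients, and the six Part 1 patients at that dose enter the first stage of the Simon design. Losing DLT patients from the count lowers the observed DLT rate, which favours the higher dose level.

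**Working it through.** **The plan's own figures.** The evaluation period is a 7-day lead-in plus 28 days (4.1), so 35 daily doses. 0.60 × 35 = 21 doses, as stated. Three levels × 6 patients = 18, the stated Part 1 maximum. Both reproduce. The plan gives no operating characteristics for the 3+3.

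**Who can fall below 60%.**
- A patient whose last dose is on day 14 has 14/35 = 40% of planned doses. If tablets stop being expected once treatment stops, compliance is 14/14 = 100%. Section 6.2.3 does not say which applies.
- A 14-day hold, the limit in 7.2 before discussion with the Principal Investigator, leaves 35 − 14 = 21 doses, exactly 60%. One more missed dose gives 20/35 = 57%.
- The schedule of events allows a 5- to 10-day lead-in, so 33 to 38 planned doses and a 60% threshold of 19.8 to 22.8. With a 5-day lead-in, a 14-day hold leaves 19/33 = 58%.
- Twice-weekly ECP over cycle 1 is 8 sessions, and 60% of 8 is 4.8. The stated minimum of 4 sessions is 50%, so the ECP count and its percentage also disagree.

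**Effect on one cohort.** Six patients at a level have two DLTs, and one DLT patient is below 60%. Under 12.2.1 the count is 2/6, which exceeds the MTD. Under the second sentence of 12.3 that patient is replaced, and if the replacement has no DLT the count is 1/6 and the level is the RP2D.

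**Acceptance probability.** Let p be the true DLT rate and b(k) the probability of k DLTs in 3 patients. From Table 2,

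P(level is RP2D) = b(0)[b(0) + b(1)] + b(1)b(0),

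which equals the probability of at most 1 DLT in 6. At p = 0.30, b(0) = 0.343 and b(1) = 0.441, so P = 0.343 × 0.784 + 0.441 × 0.343 = 0.420.

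If a share f of DLT patients is replaced, the counted DLT rate becomes p(1 − f)/(1 − pf). At p = 0.30:
- f = 0.25: 0.225/0.925 = 0.243, so P = 0.550
- f = 0.50: 0.150/0.850 = 0.176, so P = 0.713

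| True DLT rate (assumed) | All DLTs counted | f = 0.25 | f = 0.50 |
|---|---|---|---|
| 20% | 0.655 | 0.758 | 0.863 |
| 30% | 0.420 | 0.550 | 0.713 |
| 40% | 0.233 | 0.351 | 0.534 |

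**Non-DLT patients with toxicity-related missed doses.** The second sentence of 4.2 does not replace them. The first sentence of 4.2, and 12.2.1, make them non-evaluable, and 12.3 replaces them. Here replacement is the stricter rule. Suppose 25% of patients have a DLT and a further 15% miss more than 40% for related non-DLT toxicity (both assumed). Counting the latter as evaluable without a DLT gives P = 0.534. Replacing them gives a counted rate of 0.25/0.85 = 0.294 and P = 0.433.

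**The case against.** The authors plainly meant to count DLTs. The first sentence of 12.3 and 12.2.1 both say so, and 4.2 protects doses missed to manage related toxicity. A reader might infer that the plan discards every patient stopped by an early DLT. The documents do not support that: the first sentence of 12.3 addresses exactly that patient, so what exists is a conflict within 12.3, and only on one reading of compliance. With uniform DLT onset over 35 days and every DLT patient stopping drug, 20/35 of DLTs would fall before dose 21, and acceptance at a 40% rate would be 0.60. That figure needs both assumptions and also requires the exemption to be ignored.

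The interaction case needs a chain of events: a DLT, continuation with approval, a potent inhibitor although 6.6.2 recommends agents with less inhibition, and a reduction inside the window. The 7.1 sentence can also be read as saying only that such a reduction is not itself a DLT. These points make the case rare, but they do not settle what happens when it occurs.

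There are backstops. The medical monitor is notified of each DLT, and medical monitor and DSMC approval is needed before cohort expansion. In Part 2, Table 11 gives a stopping probability of 0.818 and an expected sample size of 23.6 at a 30% rate, so it should not be inferred that a too-toxic level would usually run through the full expansion. Both are partial. The DSMC would be applying contradictory rules. Part 2 monitoring acts only after more patients are treated, and its boundary counts non-hematologic events, whereas Table 3 also includes hematologic DLTs.

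The toxicity-related missed-dose conflict for non-DLT patients is narrow. An adverse reaction leading to dose reduction or withdrawal is already a DLT in Table 3, and a 14-day hold on the 7-day lead-in stays at 60%. It should not be presented as another route to accepting too high a dose, because there 12.3 is the stricter rule.

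**Conclusion.** The contradiction is in the current text and can change the RP2D. It is a failure of internal consistency, not evidence that the design sets out to drop DLTs. It leaves unprotected the DLT patient who stays on with held doses and the DLT patient with an interaction-driven reduction. For the patient stopped by an early DLT, the two sentences of 12.3 can conflict.

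One replaced patient is enough to move a level from 2/6 to 1/6. The direction is certain: removing DLT patients can only lower the counted rate. The size is not. The rise from 0.42 to 0.55 or 0.71 at a 30% true rate rests on assumed rates and replaced shares, and with every DLT counted, as 12.2.1 directs, the figure stays at 0.42.

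**What to change.** State in 12.3 and 7.1, consistent with 12.2.1, that a patient with a DLT in the evaluation period is always evaluable and never replaced, whatever the compliance or concomitant-medication dose reduction.

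Separately, reconcile both sentences of 4.2 with 12.2.1 and 12.3 into one rule for patients without a DLT who miss more than 40% of treatment because of related toxicity. This is a trade-off: counting them as evaluable without a DLT makes a level easier to accept (0.53 against 0.43 in the illustration above), while replacing them discards patients whose missed doses were themselves caused by toxicity. The choice should be explicit. In the same edit, say whether compliance in 12.3 is measured against all planned doses, and align the ECP count with its percentage.

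The cost is wording only, with no new procedures. The DLT clarification may reject a dose level that the literal second sentence of 12.3 would have accepted.
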